11. SAMPLE SIZE CALCULATIONS & POWER ANALYSIS

The sample size is calculated and powered to look at multiple comparisons, between arms A and B, A and C plus B and C with a hypothesized higher increase with addition of Azithromycin to infant with Afzaaish in LW. Also, adjustment for multiple comparison is needed. Thus, calculations for the sample size is estimated and are per arm sample size is provided below based on the primary outcome of length velocity in LW trial with 1-sided testing, alphas to account for multiple comparison (the lower alpha), and drop out of 14% is assumed in the trial.

Assumptions for Sample Size Calculations

Variable	Difference	Std Dev	Alpha	Drop out portion	n/arm	n/arm adj dropout	Actual Power
Length Velocity	0.12	0.5	0.025	0.14	274	319	0.801

Based on assumptions, a sample size of 319 children per arm is calculated, assuming 14% drop out rate (i.e. 10% margin for loss to follow up, and 4% infants deaths).

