The null hypothesis for this trial is that the mean difference in length velocity between an infant of a lactating woman receiving standard breastfeeding counseling with BEP alone (Intervention arm 1) for 6 months or in combination with a single prophylactic dose of azithromycin at 42 days of age (Intervention arm 2) and an infant of a lactating woman receiving standard breastfeeding counseling alone (control arm) is equal or less than 0.12 cm/month (primary outcome). Due to the absence of evidence of such interventions on length velocity, we based this hypothesis on our local experience and field data from our field sites. The alternate hypothesis for this trial is that an infant of a lactating woman receiving BEP alone for 6 months or in combination with a single prophylactic dose of azithromycin at 42 days of age has a mean length velocity is greater than 0.12 cm/month that of an infant of a lactating woman not receiving an intervention at 6 months. The sample size takes multiple comparisons into account and is based on the primary outcome of length velocity with an effect size of difference of 0.12 cm per month between the arms (i.e., 0.72 cm difference at 6 months), a 1-sided test, power of 80% and an alpha of 0.025 to account for multiple comparisons (the lower alpha – Bonferroni correction was used). A drop-out rate of 14% (i.e., 10% loss to follow up and infant mortality rate of 4%) is assumed in the study, so the minimum total sample size required is 957 (319 lactating women in each arm).

7. Eligibility criteria

Inclusion Criteria

- a) Lactating women with a mid-upper-arm-circumference (MUAC) of < 23.0 cm
- b) Infants with a live birth outcome, captured within 168 hours (0-6 days)
- c) Individuals with the intention to stay in the catchment area for entire duration of trial after enrollment
- d) Individuals with the intention to exclusively breastfeed child for at least 6 months of age
- e) Individuals who have provided voluntary written informed consent

Exclusion Criteria

- a) Newborns with a birth weight of less than 1500 grams
- b) Newborns with a known congenital anomaly or other severe illness based on the study physician's assessment before enrollment.
- c) Lactating women with known allergies to peanut, lentils, chickpea or dairy products
- d) Individuals who were previously enrolled in the trial

8. Blinding

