The primary analysis will be by intention-to-treat (ITT) perform for those who had anthropometry at 6 months. All analyses will be done using Stata software version 16. The WHO 2009 Child Growth Standards will be used for age-sex standardization of child length, weight, head circumferences, MUAC and weight-for-height. Descriptive analysis of each arm will be conducted, and percentages or continuous data with SD will be reported.

The baseline characteristics will be assessed by arm. Outcomes of mean length velocity, growth velocity, weight gain, z scores and change in z score from 0-6 month will be compared using one way analysis of variance (ANOVA). Tukey's test will be used for multiple comparisons. As determined *a priori* the analysis will be adjusted for the birth weight and length of infant, maternal MUAC at enrollment, maternal age, gravida, maternal body mass index and gender of child using general linear model (GLM). Mixed model analysis will be used to compare change in outcome per month in the intervention arm compared to the control arm. Using repeated measures ANOVA, the analysis will report beta coefficients and 95% CI. The coefficients represents the rate of change in outcome per month. For covariate adjustment, an unadjusted and stepwise adjusted model will be run. Trajectories will be plotted for mean length and weight by age for each arm, and monthly z scores were also be plotted.

13. Potential sub-group analysis

The following variables will be considered for sub-group analysis for primary and secondary outcomes:

1. Birth weight i.e. <2500 gm and => 2500 gm
2. Maternal MUAC at enrolment i.e. < 21.0 cm and =>21.0 cm
3. Maternal age i.e. <30 years and => 30 years
4. Gravidity i.e. <3 and =>3
5. Maternal BMI i.e. <18.5 kg/m² and =>18.5 kg/m²
6. Gender of child

14. Missing Data

We will treat missing data as it is, no imputation will be applied. We discussed that due to growth flattering during this age, imputation maybe unreliable.

15. Interim analysis

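### The SAP's no-imputation rule makes no exception for baseline covariates, so the adjusted model can lose infants whose length velocity was measured

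*SAP*

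**What the plan says.** SAP section 14 (Missing Data) states: "We will treat missing data as it is, no imputation will be applied". The reason given is that "due to growth flattering during this age, imputation maybe unreliable". The section does not separate outcomes from covariates.

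SAP section 12 restricts the primary intention-to-treat analysis to infants with 6-month anthropometry; complete covariates are not required. It compares arms by one-way ANOVA with Tukey's test. It then says that "the analysis will be adjusted for the birth weight and length of infant, maternal MUAC at enrollment, maternal age, gravida, maternal body mass index", plus the child's sex, in a general linear model: seven covariates, chosen in advance. It adds: "For covariate adjustment, an unadjusted and stepwise adjusted model will be run". It does not say whether the ANOVA or the adjusted model is the primary test.

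Protocol section 10 (Analysis approach) provides group-mean imputation for a missing outcome and says nothing about a missing covariate. On attrition, SAP section 6 says: "A drop-out rate of 14% (i.e., 10% loss to follow up and infant mortality rate of 4%) is assumed in the study".

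**The concern.** A regression fitted to data left as they are omits every record with a missing covariate. An infant with both lengths measured belongs to the SAP's own analysis set, but can still disappear from the adjusted comparison because, say, the mother's gravidity was not recorded. The reason given for not imputing does not reach this case: uncertain growth is an argument about missing measurements of growth, not about a missing maternal age or BMI.

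Two things are at stake. The first is precision: the adjustment is meant to add some, and deleting infants takes some back. The 14% allowance covers only loss to follow-up and death, so nothing is set aside for this. The second is comparability. If the sample shrinks as covariates enter, a change in the estimate between the unadjusted and adjusted models mixes the effect of adjustment with a change of infants. That problem exists however small the power loss is.

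**Working it through.** **Inputs**
- Difference: "an effect size of difference of 0.12 cm per month between the arms" (SAP section 6).
- Test: "a 1-sided test, power of 80% and an alpha of 0.025 to account for multiple comparisons" (SAP section 6).
- SD 0.5, 274 evaluable per arm, 319 after dropout, power 0.801: the row "Length Velocity 0.12 0.5 0.025 0.14 274 319 0.801" (Protocol section 11).
- Missingness per covariate: not in the documents. Assumed 0.5%, 1% or 2%, independent between items.

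**Step 1. Reproduce the plan's figures.** For a two-sample t-test, the noncentrality is 0.12 / (0.5 × √(2/n)). At n = 274 this is 2.809, and one-sided power at alpha 0.025 is 0.801; at n = 273 it is 0.799. So 274 per arm and 0.801 both reproduce. Dropout: 274 / 0.86 = 318.6, rounded up to 319. Evaluable total: 3 × 274 = 822.

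**Step 2. Which covariates can be missing when the outcome is present?**

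| Covariate | Can it be missing while length velocity is measured? |
|---|---|
| Infant length | No, if it is the baseline (day 0–6) length, which is part of length velocity (SAP 10.1) |
| Birth weight | Unlikely: a weight is needed to apply the 1500 g exclusion (SAP 7) |
| Maternal MUAC | Unlikely: it is an entry criterion (SAP 7) |
| Child's sex | Unlikely: it is needed for the z-scores |
| Maternal age | Yes |
| Gravidity | Yes: self-reported (SAP 10.5) |
| Maternal BMI | Yes |

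Three items are realistically at risk. Birth weight and length would join them only if they mean values at delivery rather than the 0–6 day measurements; the SAP does not define this.

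**Step 3. Infants lost and power.** Fraction retained = (1 − m)³; n per arm = 274 × (1 − m)³; power as in step 1.

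| m per item | Retained | Lost of 822 | n per arm | Power before any gain from adjustment |
|---|---|---|---|---|
| 0 | 1.000 | 0 | 274 | 0.801 |
| 0.5% | 0.985 | 12 | 270 | 0.795 |
| 1% | 0.970 | 24 | 266 | 0.789 |
| 2% | 0.941 | 48 | 258 | 0.776 |

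**Step 4. Offset from adjustment.** Covariates that explain a share R² of the outcome variance multiply the SD by √(1 − R²). The adjusted model breaks even with the full unadjusted one when R² is about equal to the fraction lost: 1.5%, 3.0% or 5.9% in the three rows. With 2% missing per item and an assumed R² of 0.10, the SD is 0.5 × √0.9 = 0.474 and power at 258 per arm is 0.818, above the planned 0.801.

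**The case against.** The strongest case on the other side is that this is a wording gap with little practical effect. The stated 80.1% power belongs to an unadjusted two-group comparison. The one-way ANOVA uses no covariates and keeps every infant with an outcome, and the main results shell (Table 3 in SAP section 17) has no column for adjusted results. SAP section 11 provides weekly data queries and repeat home visits, and gravidity can simply be asked again, so missing items should be few. If they cluster in the same women, the loss is smaller still. The shrinking-sample problem can also be handled without imputation, by fitting all steps on a common set of infants and reporting n.

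Most of this stands, and it limits the size of the point. It does not supply the missing rule. The adjusted model was chosen in advance and the SAP does not rank it below the ANOVA, so it cannot be set aside as secondary. A common complete-case sample would restore comparability, but only by discarding observed outcomes from the unadjusted model too.

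A reader might go further and infer that any one of the seven covariates could remove an infant. Taking the exponent as 7 gives losses of 28, 56 or 108 infants and power of 0.787, 0.772 or 0.743. The documents do not support that reading: it counts items that are part of the outcome, or are needed for eligibility or the z-scores.

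**Conclusion.** The gap is real and minor. Followed as written, SAP section 14 removes infants with an observed primary outcome from the pre-specified adjusted model, for a reason that does not apply to covariates, and may leave the unadjusted and adjusted estimates resting on different infants. Under the assumed 0.5% to 2% independent missingness on three items, the loss is 1.5% to 5.9% of evaluable infants, or about 0.6 to 2.4 percentage points of power before any gain from adjustment.

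These sizes rest entirely on assumed missingness. A reader might infer that the trial ends up underpowered; the documents do not show this. The ANOVA is unaffected, and a modest R² would offset the loss in the adjusted model. The firmer grounds for acting are comparability between models and having the rule fixed before unblinding.

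**What to change.** Limit the no-imputation rule in SAP section 14 to outcomes and their components, including baseline length and any other baseline measurement used to compute the outcome being analysed. Without that carve-out, filling a missing baseline length would amount to imputing length velocity. Then add:

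> For other baseline covariates, a missing value is replaced by the mean (or most frequent category) over all arms combined, without reference to arm, so that every infant with an observed outcome is in both the unadjusted and adjusted models; n is reported for each model.

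Baseline values precede treatment, so a fill-in that ignores arm does not bias the randomised comparison. SAP section 12 should also say which model is primary, and whether birth weight and length mean delivery values or the 0–6 day measurements.

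The cost is a short SAP edit and a few lines of code. The downside is slightly less explanatory power for a covariate in the few infants with a filled value.

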While stopping rules will be utilized to help the DSMB to assess the justification of trial continuation, the DSMB will take into account the balance of risks and benefits as well as consistency with external evidence. Thus, the DSMB recommendation to continue or discontinue will not be based on any single issue or value in any of the analyses, but a comprehensive analysis taking into account multiple issues around the trial.

The DSMB may recommend termination or modification of the study if:

- i. In an interim analysis, there is strong evidence of a benefit (increases length velocity and/or secondary outcome) from the study intervention (O'Brien Fleming rule, $p < 0.005$).
- ii. In an interim analysis, there is strong evidence of harm (incidence of SAEs) from the study intervention. For harm assessment, no fixed statistical rules will be applied, but the DSMB will holistically consider point estimates and confidence intervals for SAE incidence differences, p-values from appropriate statistical tests and other relevant factors, when determining its recommendation about study continuation or discontinuation.

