Data Safety and Monitoring Board of the trial will request an independent statistician to run interim analysis when 50% of the enrollment will complete the 6 months follow-ups in the trial. The analysis will be coded, and the findings will on difference in primary, secondary outcomes and Serious Adverse Events will be shared to DSMB in blinded coding. The DSMB will review results from the interim data analysis and will determine whether stopping boundaries have been crossed. Additional interim analyses may be completed and reviewed by the DSMB, per the advisement of the DSMB chair. The DSMB may, at its own discretion, ask the interim analysis to be done earlier or additional interim analyses to be completed on an ad hoc basis. Based on the trial safety monitoring and interim analysis, the following may be the key decision/s of DSMB pertaining to the trial:

- i. No action needed; trial continues as planned.
- ii. Early stopping due, for example, to clear benefit or harm of an intervention/s, uselessness, or external evidence.
- iii. Extending recruitment (based on actual control arm response rates being different to predicted rather than on emerging differences) or extending follow-up.
- iv. Stopping an arm of the multi-arm trial.
- v. Sanctioning and/or proposing protocol changes

While stopping rules will be utilized to help the DSMB to assess the justification of trial continuation, the DSMB will take into account the balance of risks and benefits as well as consistency with external evidence. Thus, the DSMB recommendation to continue or discontinue will not be based on any single issue or value in any of the analyses, but a comprehensive analysis considering multiple issues around the trial.

The DSMB may recommend termination or modification of the study if:

- i. In an interim analysis, there is strong evidence of a benefit (increases length velocity and/or secondary outcome) from the study intervention (O'Brien Fleming rule, $p < 0.05$).

- ii. In an interim analysis, there is strong evidence of harm (incidence of SAEs) from the study intervention. For harm assessment, no fixed statistical rules will be applied, but the DSMB will holistically consider point estimates and confidence intervals for SAE incidence differences, p-values from appropriate statistical tests and other relevant factors, when determining its recommendation about study continuation or discontinuation.

16. Background characteristics of participants

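### SAP section 15 gives the O'Brien-Fleming interim benefit threshold as p < 0.05, the protocol gives p < 0.005, and no overall alpha used in the documents produces the SAP figure

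*SAP*

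**What the plan says.** Both documents plan one interim analysis, triggered "when 50% of the enrollment will complete the 6 months follow-ups in the trial", and let the DSMB ask for earlier or extra looks. At the interim the DSMB "will determine whether stopping boundaries have been crossed".

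The benefit criterion appears in both documents in the same words, apart from the number:

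- SAP section 15 (Interim analysis): "strong evidence of a benefit (increases length velocity and/or secondary outcome) from the study intervention (O'Brien Fleming rule, $p < 0.05".
- Protocol section 10 (Stopping guidelines / Stopping rules): "strong evidence of a benefit (increases length velocity and/or secondary outcome) from the study intervention (O'Brien Fleming rule, $p < 0.005".

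Both also say that the DSMB's recommendation "will not be based on any single issue or value in any of the analyses". Harm has no fixed statistical rule.

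The design level is in SAP section 6: "a 1-sided test, power of 80% and an alpha of 0.025 to account for multiple comparisons". Protocol section 11 has the same alpha and sidedness. SAP section 12 adds that "Tukey's test will be used for multiple comparisons". Neither document gives the overall alpha of the stopping rule, the sidedness of the interim p, whether that p is Tukey-adjusted, the level left for the final test, or a spending function.

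**The concern.** A DSMB holding both documents has two benefit boundaries that differ tenfold. An O'Brien-Fleming rule is strict early and leaves the final test almost untouched; a nominal 0.05 at half the information does neither. An unadjusted two-sided p < 0.05 in the favourable direction is 1-sided 0.025, so it would use at the interim the whole 1-sided alpha that the sample size allots to one comparison. Tukey's test adjusts for the three arm pairs, not for a second look.

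Two things are at stake: the false-positive rate if a crossing leads to stopping or a claim, and whether the DSMB is told that a given interim result has crossed at all.

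**Working it through.** **Inputs.** Difference 0.12 cm/month, SD 0.5, alpha 0.025 1-sided, 274 per arm evaluable, 319 per arm enrolled (Protocol section 11; SAP section 6). Interim at 50% of enrolment with 6 months completed.

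**Design reproduced, null difference of zero.** n = 2 × (0.5 × (1.960 + 0.842) / 0.12)² = 272.5, or 273 per arm by the normal approximation. At 274 per arm the t-based power is 0.8007 (stated 0.801), and 274 / 0.86 = 318.6, or 319. The sample size therefore rests on a null of zero, and the figures below do too.

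**Information at the interim.** Half of 274 is 137 per arm, t = 0.50. If the trigger means half of the 319 enrolled, all with data, that is about 160 per arm, t = 160/274 = 0.58.

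**O'Brien-Fleming boundary.** With corr(Z1, Z2) = √t, solve P(|Z1| > c/√t or |Z2| > c) = 0.05 for c.

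| t | interim z | interim two-sided p | final z | final two-sided p |
|---|---|---|---|---|
| 0.50 | 2.797 | 0.0052 | 1.977 | 0.0480 |
| 0.58 | 2.604 | 0.0092 | 1.990 | 0.0466 |

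The 1-sided interim p at t = 0.50 is 0.0026. The protocol's 0.005 is the rounded two-sided value. A Lan-DeMets O'Brien-Fleming-type spending function at 1-sided 0.025 gives two-sided 0.0031 then 0.049 at t = 0.50, and 0.0067 then 0.048 at t = 0.58. The classic interim p reaches 0.05 only with an overall two-sided alpha of 0.184 (t = 0.50) or 0.151 (t = 0.58). Neither document uses such a level.

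**Chance of a false benefit claim.** One comparison, one endpoint, t = 0.50: P(Z1 > a) + P(Z1 ≤ a, Z2 > b) under no difference.

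| Interim, then final | Interim + final part | Total |
|---|---|---|
| two-sided 0.05, 0.05 | 0.0250 + 0.0166 | 4.2% |
| two-sided 0.005, 0.05 | 0.0025 + 0.0234 | 2.6% |
| two-sided 0.005, 0.048 | 0.0025 + 0.0225 | 2.5% |
| 1-sided 0.05, 0.025 | 0.0500 + 0.0125 | 6.2% |
| 1-sided 0.005, 0.025 | 0.0050 + 0.0223 | 2.7% |

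**Results on which the documents disagree.** At 137 per arm, SE = 0.5 × √(2/137) = 0.0604. With an unadjusted two-sided p the cut-offs are 1.960 × 0.0604 = 0.118 and 2.807 × 0.0604 = 0.170 cm/month. An observed difference between them crosses under the SAP but not under the protocol.

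**Chance of crossing if the true difference is 0.12.** 0.12 / 0.0604 = 1.986. SAP: 1 − Φ(1.960 − 1.986) = 51%. Protocol: 1 − Φ(2.807 − 1.986) = 21%. With a Tukey-adjusted p the pair is 36% and 12%; with a 1-sided p it is 63% and 28%. The gap is large on every reading.

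**The case against.** **The rule is advisory.** True: the DSMB may recommend, and will not act on a single value. The error rates are therefore conditional on a crossing leading to stopping or to a claim. But the DSMB must still determine whether boundaries were crossed, and it needs one boundary for that.

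**0.05 may be the overall alpha, or a dropped zero.** Either is possible. The sentence does not say overall alpha, and the figure stands inside an interim criterion where the protocol puts a nominal p. If overall alpha was meant, the SAP gives no interim boundary and still conflicts with the protocol. If it is a slip, it is a slip in the stopping threshold.

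**The protocol's figure is not fully specified either.** This stands. Its 0.005 fits a two-sided p; read as 1-sided it is looser than the 0.0026 that the 1-sided 0.025 design gives. A reader might infer that the SAP should simply be set to two-sided 0.005, but neither document states that the interim p is two-sided.

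**The error could be overstated.** A reader might infer that false benefit claims reach 8.3%. That is the two-directional rate for 0.05 at both looks; the rule covers benefit only, so the figure is 4.2%. A reader might also infer that an O'Brien-Fleming boundary near half the information can never equal 0.05. It can, at the overall alphas of 0.184 or 0.151 shown above; the claim holds only for the alphas that the documents use.

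**Conclusion.** The SAP threshold is wrong as written and should be corrected before any interim analysis. It contradicts the protocol, and it is about ten times the two-look O'Brien-Fleming value at 50% information for the design's own level (0.05 against 0.0052); at 58% information it is still more than five times that value (0.05 against 0.0092).

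If a crossing is acted on, the false benefit rate for one comparison is 4.2% rather than 2.5% to 2.6% on the two-sided reading, and 6.2% rather than 2.7% on the 1-sided reading. The conflict also decides whether an observed difference of about 0.118 to 0.170 cm/month counts as a crossing, a range that begins just below the design effect.

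Assumptions: a null difference of zero, SD 0.5, one endpoint, one pair, one interim look at 50% information and, for the range, an unadjusted two-sided p. These are not the operating characteristics of the whole written rule, which also admits secondary outcomes and ad hoc looks. SAP section 6 words the null as a difference that "is equal or less than 0.12 cm/month (primary outcome"; if the interim test used that null, the range would move up by 0.12, to 0.238 to 0.290.

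**What to change.** Replace p < 0.05 in SAP section 15 so that both documents give one interim boundary consistent with O'Brien-Fleming. The protocol's 0.005 matches the classic two-sided value at 50% information. In both documents state the overall alpha, the sidedness of the interim p, whether it is Tukey-adjusted, and the matching final level.

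Name one boundary method in advance and apply it at whatever information is realised:

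- classic O'Brien-Fleming: two-sided 0.0052 then 0.048 at 50%; or
- Lan-DeMets O'Brien-Fleming-type spending: 0.0031 then 0.049 at 50%, 0.0067 then 0.048 at 58%. This also covers looks that the DSMB adds.

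Do not mix them. Using 0.005 at exactly 50% and the spending function otherwise would give 0.0034 at 51%, a stricter boundary with more data.

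The cost is an SAP edit and a short protocol clarification. With 0.005 then 0.048, power for 0.12 cm/month at 274 per arm moves from about 80.2% to 79.9% for one unadjusted pair. Sample size and visits do not change. Limiting the benefit boundary to length velocity is an optional improvement, not part of this error.

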¶ Wasting was defined as a weight-for-height z score lower than -2 SD.

[figure not shown]
|| Underweight was defined as a weight-for-age z score lower than -2 SD.

Table 3 | Outcomes at 6 months in the Intention-to-treat analysis*

[figure not shown]
Outcomes	Standard of care and only exclusive breastfeeding counselling	BEP with standard of care and exclusive breastfeeding counselling	BEP plus single dose of azithromycin to infant with standard of care and exclusive breastfeeding	Pairwise comparison $\Delta \pm SD$	p-value
	N=	N=	N=		
Primary outcomes - Mean					
Length velocity of infant (cm/mon)					
Secondary outcomes					
Infant related					
Growth – Mean					
Growth velocity (gm/kg/day)					
Mid-upper-arm-circumference (cm)					
Head circumference (cm)					
Length-for-age z-score					
Weight-for-age z-score					
Weight-for-length z-score					
Head circumference-for-age z-score					
Nutritional status - no./total no. (%)					
Wasting					
Stunting					
Underweight					
Adverse event - no./total no. (%)					
Infant deaths					
Hospitalization					
Injectable therapy					
Maternal related					
Nutritional status - Mean					
Maternal weight gain (kg)					
Mid-upper-arm-circumference (cm)					
Body mass index (kg/m ²)					
Adverse event - no./total no. (%)					
Infant deaths					
Hospitalization					
Injectable therapy					

* Plus–minus values are means \pm SD.

Figure 2 | Monthly trends for z-scores
2a | Monthly mean length-for-age z-scores

2b | Monthly mean weight-for-age z-scores

2c | Monthly mean weight-for-length z-scores

[figure not shown]

Table 4 | Subgroup analysis

Indicator	1	2	3	Δ	P-value	1	2	3	Δ	P-value	1	2	3	Δ	P-value	1	2	3	Δ	P-value	1	2	3	Δ	P-value					
Subgroups	Mean length velocity (cm/mon)					Weigh gain (gram/month)					Mean MUAC					Mean length-for-age z-score					Mean weight-for-length z-score					Mean weight-for-length z-score				
Maternal MUAC	< 21.0 cm																													
	=>21.0 cm																													
Maternal BMI	<18.5																													
	=>18.5																													
Birth weight	<2500 gm																													
	=> 2500 gm																													
Maternal age	<30 years																													
	=> 30 years																													
Gravidity	<3																													
	=>3																													
Gender	Male																													
	Female																													

References

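### The SAP's Table 3 shell attaches an SD to the pairwise between-arm difference, and no confidence interval is stated for the ANOVA/Tukey or GLM comparison of length velocity

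*SAP*

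**What the plan says.** SAP section 17 gives Table 3 as the shell for the six-month intention-to-treat outcomes, with length velocity as its first row. There are three arm columns, then one headed "Pairwise comparison $\Delta \pm SD", then a p-value. The table's footnote reads "Plus–minus values are means \pm SD". That suits the arm columns and gives the SD in the difference column no other meaning.

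SAP section 12 describes the analyses behind the table:

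- Mean length velocity and the other continuous growth outcomes "will be compared using one way analysis of variance (ANOVA"), and "Tukey's test will be used for multiple comparisons".
- An adjusted general linear model is also planned.
- No interval is named for either of these.
- For the mixed-model analysis the section says "Using repeated measures ANOVA, the analysis will report beta coefficients and 95% CI", and adds "The coefficients represents the rate of change in outcome per month".

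The protocol's analysis approach (section 10) names no interval for the growth outcomes. In SAP Table 4 (subgroups), the comparison columns hold only a difference and a p-value.

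**The concern.** The SD of length velocity says how much infants differ from one another, and it does not shrink as more are enrolled. The uncertainty of a difference between two arm means is its standard error, best shown as a confidence interval. A ± SD printed after the difference invites the reader to take it as an error bar, and a clear effect could then look null.

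This matters here because the hypotheses concern the size of the difference. SAP section 6 plans on an "effect size of difference of 0.12 cm per month between the arms", and SAP section 4 sets the null and alternative on either side of that value. A Tukey p-value tests a difference of zero. It does not show where the estimate stands against 0.12, and after a non-significant result it does not show whether 0.12 has been ruled out. The secondary hypotheses for growth velocity and the Z-scores are also stated as margins, and those outcomes are reported in the same column.

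The column also runs down through wasting, stunting, underweight and adverse events. These are counts and percentages, to which a mean difference ± SD does not apply.

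**Working it through.** **Inputs.** Difference 0.12 cm/month, SD 0.5 cm/month, alpha 0.025, dropout 14%, 274 per arm before dropout and 319 after, power 0.801 (protocol section 11: "Length Velocity 0.12 0.5 0.025 0.14 274 319 0.801"). One-sided test (protocol section 11; SAP section 6). Three arms, 1:1:1 (SAP section 9).

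**Step 1: reproduce the plan's figure.**

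- Normal approximation: n = 2 × (1.960 + 0.842)² × 0.5² / 0.12² = 272.5, so 273 per arm.
- The noncentral t gives 274 per arm, with power 0.8007.
- Dropout: 274 / 0.86 = 318.6, so 319 per arm, and 3 × 319 = 957.

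The plan's figures reproduce, so SD 0.5 and n = 274 are a sound basis for what follows.

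**Step 2: uncertainty of a pairwise difference at 274 completers per arm.**

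- SE = SD × sqrt(2/n) = 0.5 × sqrt(2/274) = 0.0427 cm/month.
- Error df = 3 × 274 − 3 = 819.
- Ordinary 95% half-width = 1.963 × 0.0427 = 0.084.
- Tukey simultaneous 95% half-width = (3.3205/√2) × 0.0427 = 2.348 × 0.0427 = 0.100.

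**Step 3: what a reader would see if the observed difference were exactly 0.12.**

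| Presentation | Entry (cm/month) |
|---|---|
| Difference ± SD, if SD is the between-infant SD | 0.12 ± 0.5 |
| Difference ± SD, if SD is that of a difference between two infants, 0.5 × √2 | 0.12 ± 0.71 |
| Difference (ordinary 95% CI) | 0.12 (0.036 to 0.204) |
| Difference (Tukey 95% CI) | 0.12 (0.020 to 0.220) |

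The test statistic is 0.12/0.0427 = 2.81, with an unadjusted two-sided p of 0.005 and a Tukey-adjusted p of 0.014. Either ± SD entry would therefore stand beside a p-value below 0.05 while looking like no effect. The first two rows are alternatives because the SAP does not define an SD for the difference.

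**Step 4: sensitivity.**

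- With all 319 per arm measured and SD 0.5: SE 0.0396, ordinary half-width 0.078, Tukey half-width 0.093.
- With 274 per arm and an assumed SD of 0.4 to 0.6: SE 0.034 to 0.051, ordinary half-width 0.067 to 0.100.

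The ratio of SD to SE is sqrt(n/2), which is 11.7 at 274 and 12.6 at 319 whatever the SD. The ratio only restates that an SD is not an SE. The figures that matter are the half-widths.

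**The case against.** **An interval is promised elsewhere.** SAP section 12 commits to 95% CIs for coefficients that express a monthly rate of change. For length that is cm/month, the unit of the 0.12 hypothesis. This stands, and it defeats the stronger reading that the SAP gives no interval for the effect on linear growth. It does not close the gap. The mixed model is a different analysis from the comparison of length velocity as defined in SAP section 10.1 (six-month minus baseline length over elapsed time). It is described as intervention against control, so it does not clearly cover C against B, and no table shell displays its interval.

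**The interval can be rebuilt.** Table 3 is to show N, mean and SD by arm, from which a reader can compute SE = sqrt(SD₁²/n₁ + SD₂²/n₂). This also stands, for the unadjusted difference. The information is therefore inconvenient to extract rather than lost, and it would be wrong to say that a reader cannot tell which effects are excluded. An interval from the adjusted model could not be recovered this way.

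**SD may be a slip for SE.** That is possible, but nothing in the documents says so and the footnote repeats SD. The column would need correcting in either case. It also means that 0.12 ± 0.5 is one reading of an undefined quantity, not a prediction of what will be printed.

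**It is only a sample shell.** This stands as to consequence: no test, alpha, power or sample size changes.

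A reader might also infer that Table 4 shares the error. It does not, because its columns carry no ± SD.

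**Conclusion.** The point holds as a reporting defect in the primary results table. As written, Table 3 puts the wrong measure of spread on the between-arm difference, and no confidence interval is stated for the ANOVA/Tukey or GLM comparison of the primary endpoint. At the planning values the correct uncertainty is an SE of 0.043 cm/month, with a 95% half-width of 0.084, or 0.100 under Tukey. These figures assume the planning SD of 0.5, 274 completers in each arm, equal variances and no covariate adjustment.

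The defect does not bias any estimate. The documents do not support saying that the trial will have no confidence interval for growth, given the mixed-model commitment.

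**What to change.** In SAP section 17, Table 3:

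1. Replace the comparison column with pairwise mean difference (95% CI), with separate entries for B-A, C-A and C-B.
2. Take each interval from the same model, with the same multiplicity adjustment, as the p-value printed beside it. If the Tukey ANOVA is reported, use Tukey simultaneous intervals. SAP section 12 lists the Tukey ANOVA and the adjusted GLM without saying which is primary, so the table should name the model it reports.
3. For the binary rows (wasting, stunting, underweight, adverse events), give a risk difference with its CI.
4. Keep ± SD for the within-arm columns only, and limit the footnote to those columns.
5. Add a sentence to SAP section 12 committing to these intervals.

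The cost is a table-shell edit and one or two sentences. The mean-difference intervals come from model output that will already exist; the risk differences need one further simple calculation. Adding intervals to Table 4 would be helpful but is optional and is not part of this error.
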